1.2.1.1 Non-clinical experience

1.2.1.1.1 Pharmacology

LEE011 inhibits the growth of many tumor cell types *in vitro* and *in vivo*, including mantle cell lymphoma, liposarcoma, melanoma, and carcinomas of the esophagus, breast, lung and pancreas. Regardless of the various genetic aberrations that may be present in the cancer cells, the anti-tumor activity of LEE011 requires the presence of functional retinoblastoma protein (Rb).

In the Novartis Cell Line Encyclopedia screen, MRT and neuroblastoma cell lines were among the most sensitive to LEE011. In *in vitro* pharmacology studies, LEE011 induces anti-proliferative effects in MRT (A204, G401) and neuroblastoma cell lines (SK-N-DZ, CHP212, IMR-32, KP-N-YN, KELLY, SK-N-BE(2)).

In *in vivo* pharmacology studies, LEE011 demonstrated tumor growth suppression in MRT and neuroblastoma xenograft models. ALK mutation & MYCN status in neuroblastoma cells do not appear to be associated with LEE011 sensitivity. The majority (90-100%) of MRT and neuroblastoma tumors have functional Rb.

1.2.1.1.2 Nonclinical PKs and metabolism

The PK of LEE011 was investigated in four different species: mouse, rat, dog and monkey.

After oral administration to rats, LEE011 was moderately absorbed (48 to 84%) with bioavailability ranging from 10% and 65% across animal species. Maximum serum drug concentration (C_{max}) was between 2 and 4 hours (h). The terminal half-life (T_{1/2}) of LEE011 was moderate in rodents and monkeys (2 to 7 h), and was comparatively longer (18 h) in dogs. The predicted human PK parameters based on allometric scaling were 1259 mL.min⁻¹ (75.5 L.h⁻¹) for CL/F, 2334 L for V_{ss}/F, with a T_{1/2} of around 21 hours.

The binding of LEE011 to plasma proteins was moderate (unbound fraction in plasma for humans is $30 \pm 2\%$). ^3H -LEE011 and its metabolites are extensively distributed into the organs and tissues of rats including choroid, ciliary body and meninges with the exception of the brain. The highest radioactivity concentrations were found in tissues such as pituitary gland, pineal gland, spleen, kidney and adrenal medulla with remarkably high exposure in the thyroid gland. Distribution of LEE011 and/or its metabolites into melanin-containing structures was seen in pigmented rats.

Oxidative metabolism of LEE011 is dominated by CYP3A4 with a minor contribution of about 20% by flavin-containing monooxygenase 3 (FMO3). LEE011 is a moderate substrate of P-glycoprotein (Pgp). LEE011 is a time-dependent CYP3A4 inhibitor and a reversible inhibitor of CYP1A2. LEE011 was found to inhibit the mitoxantrone-resistant protein (MXR), and human bile salt export pump (BSEP) but not rat or dog BSEP. LEQ803 (N-demethylation) is a major metabolite in the rat and monkey, the main metabolite in humans and the only metabolite in dogs. This metabolite was found to interact with hERG channels *in vitro*.

In rat ADME studies, LEE011 was predominantly excreted with bile. The elimination of unchanged drug was limited. A minor proportion of the administered dose is excreted in urine. The bulk of the administered dose (87.3%) was excreted within 24 hours.

Overall, the elimination of LEE011 may potentially be affected by co-administered drugs that inhibit or induce CYP3A4. LEE011 may inhibit CYP3A4, CYP1A2 and BSEP depending on the dose administered.

Please refer to LEE011 Investigator Brochure (IB) for additional details.

[figure not shown]
1.2.1.1.3 Safety pharmacology and toxicology

In vitro, LEE011 did not show mutagenic or phototoxic potential.

Safety pharmacology studies did not reveal any effects on CNS or respiratory functions. In the dog telemetry study, prolongation of the average QT and QTc was observed with the potential to induce premature ventricular contractions (PVCs) at higher exposure levels. LEE011 and LEQ803 likely contributed to the QT prolonging effects seen *in vivo*.

In rats and dogs, LEE011 induced bone marrow hypocellularity, lymphoid depletion, atrophy of the skin and intestinal mucosa, decreased bone formation and testicular atrophy. These are consistent with the mechanism of action of LEE011. In addition, an increased number of ovarian corpora lutea was observed in a single female dog at the highest dose tested. The liver, bile system and gall bladder (proliferative changes, cholestasis, sand-like gallbladder calculi, and inspissated bile) were identified as additional target organs of toxicity which are not likely related to the primary pharmacology of LEE011. Correlating hematological and/or biochemistry changes were seen for the effects described in the bone marrow, lymphoid system and liver. All the described changes were fully reversible in rats and dogs.

Based on its mechanism of action and preclinical toxicology studies, the major potential toxicities for LEE011 include myelosuppression, hepatic toxicity, and prolongation of the QT interval. The risk of these toxicities may be amplified by concomitant administration of strong inhibitors of CYP3A4.

Please refer to LEE011 Investigator Brochure (IB) for additional details.

1.2.1.2 Clinical experience

[figure not shown]
As of 4 February 2013, 56 patients have been treated with single agent LEE011 in the first-in-human phase I study [CLEE011X2101] in which LEE011 is administered orally, once daily for 21 days followed by a 1 week rest (28-day cycle). Doses tested include 50 mg (n=4), 70 mg (n=2), 140 mg (n=4), 260 mg (n=4), 280 mg (n=4), 350 mg (n=5), 400 mg (n=5), 600 mg (n=4), 900 mg (n=13), 750 mg (n=8), and 1200 mg (n=3). In all, 8 DLTs have been observed. DLTs include grade 3 mucositis (n=1) in the 50 mg cohort, grade 3 pulmonary embolism (n=1) in the 280 mg cohort, grade 3 hyponatremia (n=1) and prolonged grade 3/4 neutropenia (n=1) in the 400 mg cohort, grade 4 thrombocytopenia (n=1) in the 750 mg cohort, grade 3 asymptomatic QTc prolongation with grade 3 neutropenia (n=1) in the 900 mg cohort and grade 4 febrile neutropenia (n=1) and grade 4 thrombocytopenia (n=1) in the 1200 mg cohort. The grade 3 mucositis observed in the 50 mg cohort was later determined to be due to herpes simplex virus (HSV) infection. A DLT related to mucositis has not been observed since. Four cases of Grade 1 or 2 mucositis have been observed in doses up to 350 mg; mucositis has not been observed at higher doses. The grade 3 pulmonary embolism was observed in a patient with NSCLC who had diffuse bilateral lung disease and a central venous catheter. The grade 3 hyponatremia was asymptomatic and readily corrected with saline infusion.

Grade 3 or 4 neutropenia and/or thrombocytopenia not meeting DLT criteria were seen in increasing frequency starting from 600 mg up to 1200 mg. Asymptomatic grade 1 or 2 QTc prolongation were observed in increasing frequency starting at 600 mg up to 1200 mg; 1 patient (25%) in the 600 mg cohort, 2 patients (25%) in the 750 mg cohort, 4 patients (31%) in the 900 mg cohort, and 3 patients (100%) in the 1200 mg cohort. The most frequently reported treatment-related AEs include fatigue, nausea, anemia, asthenia, neutropenia, vomiting, leukopenia, increased blood creatinine, decreased appetite, diarrhea, hypoalbuminemia, lymphocytopenia, myalgia, thrombocytopenia, dizziness, erythema, hyperglycemia, mucosal inflammation and stomatitis. The majority have been grades 1 or 2 and reversible.

The MTD of LEE011 for the 3 weeks on/1 week off schedule was determined to be 900 mg. Continuous dosing with LEE011 at 600 mg was also evaluated. This dosing regimen was not well tolerated and will therefore not be pursued further. The study continues to explore intermediate doses to establish the RDE and further assess the safety, tolerability, and preliminary anti-tumor activity of LEE011.

1.2.1.3 Clinical pharmacokinetics

Preliminary PK data up to the 1200 mg dose cohort in phase I study [CLEE011X2101] haveshown slightly over-proportional increases in exposure across the dose range tested. Steady-state is reached by day 8. Accumulation ratio (Racc) calculated from AUCtau on day 21 and AUCtau after a single dose on day 1 across the studied doses of 50 to 600 mg ranged from 1.55- to 2.94-fold. Effective T1/2 (T1/2,eff) based on drug accumulation ranges from 24 hours (50 mg QD dose) to 40 hours (600 mg QD dose).

2 Rationale

2.1 Study rationale and purpose

As described in [Section 1](#), targeting the D-Cyclin/CDK axis may be an effective means of inhibiting growth of MRT and neuroblastoma. Evaluation of LEE011 in pediatric patients at this early stage in development is driven by the strong biological rationale, supporting preclinical data, and the urgent need for effective targeted therapies in these 2 indications. It has been well established that children have similar or higher threshold for toxicity when compared to adults despite multiple intensive prior therapies ([Lee 2005](#); [Kim 2008](#); [EMA 2003](#)). Safety and PK data from pediatric patients will be used to guide dose-escalation and refine dosing in this study.

Enrollment includes patients with neuroblastoma or MRT because LEE011 has shown most in vitro and in vivo activity in these 2 indications. Evidence of anti-tumor activity in these 2 indications will be used to inform future development of LEE011 in these and other pediatric tumors where this pathway may be critical for tumorigenesis. Preclinical studies showed more than 95% of MRT and neuroblastoma have an intact pRb. Therefore, pre-screening for pRb status will not be required.

[figure not shown]
The D-cyclin-CDK4/6-INK4a-Rb pathway is also disrupted in many other pediatric tumors including osteosarcoma, rhabdomyosarcoma, Ewing's sarcoma, medulloblastoma, and high grade gliomas. Gene profiling technologies are increasingly identifying pediatric patients with tumors that have these pathway abnormalities and have the potential to derive benefit from therapy with LEE011. Therefore, patients who have documented evidence of D-cyclin-CDK4/6-INK4a-Rb pathway abnormalities (e.g. cyclin D amplification, CDK4 amplification, p16 loss etc.) will be allowed to enroll in the dose escalation part of the study.

Although in preclinical studies, LEE011 does not cross the blood brain barrier (BBB), exploration of its activity in MRT and other brain tumors is considered worthwhile due to the tumors' dependency on the cyclinD/CDK pathway and the potential for LEE011 to benefit these patients who have no effective therapy. Evaluation of LEE011 in patients with primary CNS MRT is supported by evidence that the BBB in most CNS tumors is disrupted. Systemic chemotherapy has been effective in many cases ([Deeken and Loscher 2007](#)). Moreover, surgery and radiation therapy performed as initial treatment in these patients increase the likelihood that this barrier will be disrupted. The superior outcomes of doxorubicin-based regimens in MRT, a drug that does not cross the BBB, attest to this fact ([Chi et al 2009](#)).

The primary purpose of this study is to determine the MTD and/or RDE in pediatric patients, and to delineate a clinical dose to be used in future studies. This study will also assess the safety, tolerability, PK and preliminary evidence of antitumor activity of LEE011 in patients with MRT, neuroblastoma or other tumors with D-cyclin-CDK4/6-INK4a-Rb pathway abnormalities.

2.2 Rationale for the study design

This is a multi-center, open-label phase 1 study limited to patients aged 12 months to 21 years old who have MRT or neuroblastoma. Patients with both primary CNS and extra-CNS MRT will be eligible. In addition, patients who have documented evidence of D-cyclin-CDK4/6-

INK4a-Rb pathway abnormalities will be allowed to enroll in the dose escalation part of the study. Patients must have disease that has progressed following standard therapy or for which no standard treatment option exists. The study includes an expansion at the MTD and/or RDE in order to better evaluate safety, tolerability, and preliminary evidence of antitumor activity in MRT and neuroblastoma.

There will be no pre-screening for Rb in the study due to the high frequency of intact Rb in these tumor types. Rb gene status and presence of Rb protein in tumors will be determined retrospectively in those patients who enroll in the study.

This study will utilize a BLRM which is a well-established method to estimate the MTD and/or RDE in cancer patients. The adaptive BLRM will be guided by the EWOC principle to control the risk of DLT in future patients on study. This method is more likely to assign fewer patients to either sub-therapeutic or severely toxic dose levels and estimate the MTD with smaller average bias and error than the up-and-down methods such as 3+3. The use of Bayesian response adaptive models for small datasets has been accepted by EMA (“Guideline on clinical trials in small populations” February 1, 2007) and endorsed by numerous publications (Babb 1998; Neuenschwander 2008; Neuenschwander 2010), and its development and appropriate use is one aspect of the FDA’s Critical Path Initiative.

2.3 Rationale for dose and regimen selection

The MTD of LEE011 for the 3 weeks on/1 week off schedule is 900 mg. The RDE in adults will most likely be 600 mg on the same regimen. The dose from the adult Phase 1 study that will be used to calculate the starting dose in children is 600 mg/d. This is based upon review of the safety, tolerability, and PK observed at this dose level and higher. At the 600 mg/d dose in adults, LEE011 was well tolerated with an acceptable safety profile. At this dose, systemic exposures corresponding to efficacy in preclinical models was observed. On target toxicity, neutropenia, was seen but not dose-limiting. Therefore, using the 600 mg/d dose from the adult study for calculating the starting dose in children offers a high probability of beginning at an active dose and a low probability of excessive toxicity.

The first cohort of children in this trial will be treated with a dose of 280 mg/m²/d, which is 80% of the current well tolerated dose (600 mg/d) in the ongoing adult study [CLEE011X2101] divided by the average adult body surface area (BSA) of 1.72 m². Refer to Section 6.2.1 for details.

In adults, LEE011 is dosed once daily orally, and the T_{1/2}, acc ranges from 24.2 to 40 hours. This supports once daily dosing in children. LEE011 will be dosed once a day for 21 consecutive days followed by a 7-day planned break as part of each 28-day cycle of treatment consistent with the regimen used in [CLEE011X2101].

3 Objectives and endpoints

Objectives and related endpoints are described in Table 3-1 below.

[figure not shown]

Table 3-1 Objectives and related endpoints

Objective	Endpoint	Analysis
Primary		
Determine the MTD and/or RDE of LEE011	Incidence rate of DLTs in Cycle 1	Refer to Section 10.4 .
Secondary		
(1) Characterize the safety and tolerability of LEE011	(1) AEs and serious adverse events (SAEs), changes in laboratory values and electrocardiograms (ECGs).	Refer to Section 10.5 .
(2) Characterize the PK of LEE011 and any clinically significant metabolites that may be identified	(2) Plasma concentration time profiles of LEE011, PK parameters, including but not limited to AUCtau, Cmax, Tmax, CL/F, accumulation ratio (Racc), and T1/2,acc	
(3) Assess the anti-tumor activity of LEE011	(3) Overall response rate (ORR), duration of response (DOR), and time to progression (TTP) per RECIST 1.1. In addition, for neuroblastoma, response by INRC. In addition, for primary CNS tumors, response by RANO Criteria.	
Exploratory		
(1) [REDACTED]	(1) [REDACTED]	Refer to Section 10.6 .
(2) Evaluate PD effects in patients with neuroblastoma	(2) Changes in biomarkers associated with the pharmacologic activity of LEE011 ([REDACTED] by comparing pre-treatment and post-treatment samples when available.	
(3) To characterize the relationship between QTc prolongation and exposure to LEE011 and/or any of its relevant metabolites.	(3) ECG interval parameters (e.g. QTcF, QTcB, QT, QRS, RR, PR, HR), plasma concentration time profiles of LEE011 and PK parameters such as Cmin, Cmax, AUCtau	

[REDACTED]

4 Study design

[figure not shown]
4.1 Description of study design

This is a phase 1, multi-center, open-label study, with a dose escalation part followed by an expansion part. Eligible patients aged 12 months to 21 years old whose tumor has progressed following standard therapy, or for which no standard, effective therapy exists will be enrolled in the study. LEE011 will be administered orally, once daily for 21 days followed by a 1 week break (28-day cycle) at the starting dose of 280 mg/m²/d.. For the purpose of scheduling assessments and establishing the MTD/RDE, a cycle is defined as 28 days in length.

During the dose escalation part, 3-6 newly enrolled patients in successive cohorts will receive increasing doses of LEE011 with the dosing schedule specified above. A BLRM using the EWOC principle will be used to guide dose escalation. During the course of dose escalation, additional patients may be enrolled to previously tested lower dose levels that have been assessed as safe and well-tolerated if there is no slot available in the current cohort under testing. It is expected that approximately 10 patients may be enrolled and treated within this context. In all, it is anticipated that approximately 28 patients will be treated during the escalation part.

Once the MTD/RDE has been determined, the expansion part will begin to better characterize the safety, tolerability and PK profile of LEE011, as well as assess preliminary antitumor activity of LEE011. During the expansion part of the study LEE011 will be dosed at the MTD, or at a lower RDE, if the available data suggest that the MTD is not appropriate for multiple cycles of therapy. This part will include 2 arms, one restricted to neuroblastoma patients and the second to MRT patients with either CNS or extra-CNS primary. A minimum of 8 patients each will be required for CNS and extra-CNS primary MRT. Enrollment will proceed in parallel. Patients enrolled during the expansion part of the study are required to have measurable disease. Approximately 18 patients will be treated in each arm, for a total of approximately 36 patients in the expansion part.

[figure not shown]
All patients will be required to provide archival tumor biopsies (at diagnosis or relapse) unless otherwise agreed upon by Novartis and the investigator. At screening, all patients with neuroblastoma will undergo bilateral bone marrow aspirates (BMA) and/or biopsy and will be examined for presence of disease per standard institutional practice. Patients with bone marrow involvement at study entry will have repeat bone marrow evaluations for disease response at periodic intervals during the study. If feasible, pre- and post-treatment bone marrow samples (BMA and/or biopsy) will be collected from these patients. All patients with primary CNS tumors (including MRT) will be required to have a cerebrospinal fluid (CSF) sample drawn at screening and examined for presence of tumor cells unless otherwise agreed upon by Novartis and the investigator. Patients with CSF positive for disease at screening will require a repeat CSF examination for confirmation of Complete Response (CR). If CSF is collected as part of efficacy assessment or if CSF is collected as part of routine/standard care at any time after patient has received first dose of LEE011, a sample will be requested for testing LEE011 levels in the CSF. If feasible, a PK blood sample corresponding to the timing of CSF collection will also be requested.

Patients will continue to receive treatment with LEE011 until disease progression, occurrence of unacceptable toxicity that precludes any further treatment, or if treatment is discontinued at the discretion of the investigator or by patient's withdrawal of consent. All patients will have an EOT visit within 14 days of permanently discontinuing LEE011 and will be followed for 30 days after last dose of study treatment. Analysis of the study data may occur after all patients have had the opportunity to complete at least 6 cycles of treatment.

Approximately 64 patients will be treated in the entire study.

Figure 4-1 Overview of study design

4.2 Timing of interim analyses and design adaptations

No formal interim analyses are planned.

4.3 Definition of end of the study

The study data will be analyzed and reported in the primary Clinical Study Report (CSR) taking into account all patients' data of the dose escalation and expansion parts up to the time when all patients continuing to receive treatment have completed at least six cycles of treatment with LEE011, all patients have discontinued from the study, the study is terminated early, or another clinical study that can continue to provide drug becomes available and all

[figure not shown]

4. Patients must meet the following hematologic criteria:
 - a. Peripheral absolute neutrophil count (ANC) $\geq 1000/\mu\text{L}$ without growth factor support within 7 days prior to first dose of LEE011
 - b. Platelet count $\geq 75,000/\mu\text{L}$ without platelet transfusions within 7 days prior to first dose of LEE011
 - c. Hemoglobin ≥ 8.0 g/dL without blood transfusions within 7 days prior to first dose of LEE011
5. Patients with bone marrow metastatic disease who do not meet the above criteria will be eligible to enroll in the **expansion part** of the study with the following count criteria. These patients will not be evaluable for hematologic toxicity or hematologic DLT.
 - a. ANC $> 750/\mu\text{L}$ within 7 days prior to first dose of LEE011
 - b. Platelet count $> 50,000/\mu\text{L}$ (may receive platelet transfusions) within 7 days prior to first dose of LEE011
 - c. Hemoglobin ≥ 7.5 g/dL (may receive RBC transfusions) within 7 days prior to first dose of LEE011
6. Extent of disease (Refer to [Appendix 1](#), [Appendix 2](#) and [Appendix 3](#)).
 - For the **dose escalation part** of the study patients must have evaluable and/or measurable disease.
 - For the **dose expansion part** of the study patients must have at least one measurable disease as defined by RECIST v1.1. Neuroblastoma patients with positive MIBG (metaiodobenzylguanidine) scan will be eligible and considered evaluable and measurable. Neuroblastoma patients with bone marrow-only disease will NOT be eligible. If palliative XRT has been administered, at least one measurable lesion must not have been irradiated. Previously irradiated lesions must demonstrate clear evidence of progression to be considered measurable.
7. All patients should submit an archival tumor biopsy specimen (collected at diagnosis or relapse). Patients who have no tumor tissue available may be permitted to participate after discussion with Novartis and the investigator.
8. Patients must have a Lansky (≤ 16 years) or Karnofsky (> 16 years) score of at least 50. Patients who are unable to walk because of paralysis, but who are sitting up in a wheelchair, will be considered ambulatory for the purpose of assessing the performance score. (Refer to [Appendix 4](#), [Appendix 5](#)).
9. Patients must have fully recovered from the acute toxic effects of all prior chemotherapy, immunotherapy, or radiotherapy prior to enrollment.
10. Written informed consent/assent before any study-specific screening procedures. For pediatric patients, consent will be obtained from parent(s) or legal guardian(s) and the signature of at least 1 parent or guardian will be required. Investigators will also obtain assent of patients according to local, regional or national guidelines.

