10.1.3 Dose-determining analysis set

The dose-determining set consists of all patients from the safety set who either meet the following minimum exposure criterion and have scheduled safety evaluations, or experience a DLT. A patient is considered to have met the minimum exposure criterion if he received at least 16 out of the 21 planned daily doses (3 weeks on, 1 week of schedule) of LEE011 in the first 28 days of dosing.

[figure not shown]
Patients who do not experience DLT during the first cycle are considered to have sufficient safety evaluations if they have been observed for ≥ 28 days following the first dose, and are considered by both the Sponsor and Investigators to have enough safety data to conclude that a DLT did not occur.

Patients who do not meet these minimum safety evaluation requirements will be regarded as ineligible for the DDS.

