10.4.1 Variable

The primary endpoint is the incidence of DLTs in cycle 1. Estimation of the MTD of the treatment will be based upon the estimation of the probability of DLT in Cycle 1 for patients in the DDS. This probability is estimated by the model in [Section 10.4.2](#).

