10.4.2 Statistical hypothesis, model, and method of analysis

An adaptive BLRM with 2 parameters, guided by the EWOC principle, will be used to make dose recommendations and estimate the MTD/ RDE during the study. The use of Bayesian response adaptive models for Phase I studies has been advocated by the EMEA guideline on

small populations 2006 and by [Rogatko et al \(2007\)](#) and is one of the key elements of the FDA's Critical Path Initiative.

The adaptive BLRM model will be fitted on the dose-limiting data (i.e. absence or presence of DLT) accumulated in cycle 1 throughout the dose escalation part (and possibly during the dose expansion part), for modeling the dose-DLT relationship of LEE011.

The DLT relationship in the escalation part of the study will be described by the following Bayesian logistic regression model:

$$\text{logit}(\pi_{(d)}) = \log(\alpha) + \beta \log(d/d^*), \quad \alpha > 0, \beta > 0$$

where $\text{logit}(\pi_{(d)}) = \ln(\pi_{(d)}/(1-\pi_{(d)}))$, and $\pi_{(d)}$ is the probability of a DLT at dose d . Doses are rescaled as d/d^* with reference dose of $d^* = 580 \text{ mg/m}^2$. As a consequence α is equal to the odds of the probability of toxicity at d^* . Note that for a dose equal to zero, the probability of toxicity is zero.

If a different dosing schedule will be considered, a Bayesian Meta-analytic approach will be used to take into account historical data collected for the initially planned schedule in the actual study, in order to derive an informative prior estimation of the dose-toxicity relationship for the new dosing regimen. This informative prior will be combined with DLT data for the new dosing regimen using a 2-parameter BLRM.

For further details of the statistical model including specification of prior distribution for the BLRM parameters, implementation and results under a variety of data scenarios please refer to [Appendix 7](#).

Dose recommendation

[figure not shown]
Dose escalation

After each cohort of patients, the posterior distributions for the probabilities of DLT rates at different dose levels are obtained. The results of this analysis are summarized in terms of the estimated probabilities that the true rate of DLT at each dose-level will lie within each of the following intervals:

- [0, 0.166) under-dosing
- [0.166, 0.333) targeted toxicity
- [0.333, 1.00] excessive toxicity

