The overdose control criterion mandates that any dose of LEE011 for which the DLT rate has more than a 25% chance of being excessively toxic, i.e. exceeding 0.333, will not be considered for the next dose cohort. The final estimate of the MTD/RDE before the start of the expansion will also satisfy this condition.

Note that the dose that maximizes the posterior probability of targeted toxicity is the best estimate of the MTD, but it may not be an admissible dose according to the overdose criterion if the amount of data is insufficient. If vague prior information is used for the probabilities of DLT, in the early stages of the study this escalation procedure will reflect a conservative strategy.

Details of the criteria for dose escalation and the determination of the MTD are provided in [Section 6.2.2](#).

Dose expansion

Upon completion of the first cycle of treatment for at least 10 patients within the dose expansion part, if the observed DLT rate exceeds 33%, the BLRM will be re-run to confirm that the estimated MTD/RDE still satisfies the overdose criterion. If the dose fails to satisfy the criterion a change to the dose under study may be made according to the Bayesian model recommendation, after review of the clinical data.

Listing/ summary of DLTs

DLTs will be listed and their incidence summarized by primary system organ class, worst grade based on the CTCAE version 4.03, type of adverse event, and by treatment group. The dose-determining set will be used for these summaries.

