10.7 Interim analysis

No formal interim analyses are planned. However, the dose-escalation design foresees that decisions based on the current data are taken before the end of the study. More precisely, after each cohort in the dose-escalation phase, the next dose will to be chosen depending on the observed data. Details of this procedure and the process for communication with investigators are provided in [Section 6.2.2](#).

Additionally, upon completion of the first cycle of treatment for at least 10 patients within the dose expansion part, if the observed DLT rate exceeds 33%, the BLRM will be re-run to confirm that the estimated MTD/RDE still satisfies the overdose criteria of the model.

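### Must the protocol say how expansion patients who cannot be assessed for hematologic DLT count in the 33% DLT-rate check?

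*Protocol*

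**What the plan says.** Protocol inclusion criterion 5 (Section 5.2) lowers the count thresholds for patients with bone marrow metastases, in the expansion part only, and states: "These patients will not be evaluable for hematologic toxicity or hematologic DLT". Nothing there removes them from assessment for the other DLT types in Table 6-2, such as QTc, gastrointestinal and hepatobiliary events.

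Section 10.1.3 builds the dose-determining set (DDS) from safety-set patients who either "meet the following minimum exposure criterion and have scheduled safety evaluations, or experience a DLT". A patient without a DLT needs at least 28 days of observation, and the Sponsor and Investigators must agree that they "have enough safety data to conclude that a DLT did not occur".

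Section 10.4.1 bases the MTD on "the estimation of the probability of DLT in Cycle 1 for patients in the DDS". For the DLT listings and incidence tables, Section 10.4.2 says: "The dose-determining set will be used for these summaries".

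The expansion check is in Sections 10.4.2 and 10.7. It applies "upon completion of the first cycle of treatment for at least 10 patients within the dose expansion part", and then "if the observed DLT rate exceeds 33%, the BLRM will be re-run to confirm that the estimated MTD/RDE still satisfies the overdose criterion". Neither section names an analysis set for the 10 patients or for the rate. On fitting expansion data at all, Section 10.4.2 says "and possibly during the dose expansion part", whereas Appendix 7 describes a fit to both parts.

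Two other places mention these patients: Section 6.3.1 (dose modification) and Section 6.4.1 (transfusion and growth factor support in Cycle 1). Neither gives a counting rule. SAP Section 2.2 refers analysis sets to RAP Module 3 for the primary CSR, which was not supplied.

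**The concern.** A patient who can show only some types of DLT does not fit a yes/no DLT outcome. Section 10.1.3 seems to make this worse. If such a patient has a QTc DLT, the DLT clause brings the patient into the DDS. If the patient has no DLT, someone must decide whether absence of DLT can be concluded when hematologic events were never assessable. Decided one way, these patients dilute the rate. Decided the other way, they enter only when they have an event, which raises it.

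At stake is a safety prompt in a pediatric study. If the observed rate lands on the wrong side of 33% because of an unstated denominator, the model is not re-run when it should be, or is re-run without need. The sections also look uneven: the DDS is named for the model and the tables but not for the check.

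**Working it through.** **The plan's own figure.** The only calculated figure for the expansion part is in Section 10.8: 36 patients give a 97% chance of seeing at least one event with a true rate of 10%. This reproduces: 1 − 0.9^36 = 0.977. No operating characteristic is given for the 33% check.

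**Plain count.** Take 10 patients, 3 of them admitted under criterion 5 and without a DLT, and 3 DLTs among the other seven. Counting everyone gives 3/10 = 30%, so no re-run. Dropping the three gives 3/7 = 42.9%, so a re-run.

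**Probability that the check fires.** Inputs:
- 10 expansion patients in total, m of them admitted under criterion 5.
- True DLT rate p = 0.40 (assumed).
- Hematologic share of DLTs h = 1/2. In Protocol Section 1.2.1.2, 4 of 8 adult DLTs are purely hematologic. At or below 900 mg it is 2 of 6, so h = 1/3 is also shown.
- X ~ Bin(10 − m, p) DLTs in fully evaluable patients; Y ~ Bin(m, p(1 − h)) DLTs in criterion 5 patients.

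With m = 0, at least 4 DLTs are needed (3/10 = 30%, 4/10 = 40%), and P(X ≥ 4) = 0.618.

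With m = 3 and h = 1/2, X ~ Bin(7, 0.4) and Y ~ Bin(3, 0.2). P(Y = 0, 1, 2, 3) = 0.512, 0.384, 0.096, 0.008. P(X ≥ 1, 2, 3, 4) = 0.972, 0.841, 0.580, 0.290.
- *Counted as ordinary patients*, (X + Y)/10: 0.512 × 0.290 + 0.384 × 0.580 + 0.096 × 0.841 + 0.008 × 0.972 = 0.460.
- *Dropped*, X/7: P(X ≥ 3) = 0.580.
- *Entered only with a DLT*, (X + Y)/(7 + Y): 0.512 × 0.580 + 0.384 × 0.841 + 0.096 × 0.972 + 0.008 × 0.972 = 0.721. If 33% is read as one third, 3/9 no longer exceeds it and the result is 0.709.

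The same enumeration over a range, always with 10 patients in total (the value in brackets applies where a cut-off of one third changes the result):

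| p | h | m | Ordinary | Dropped | Only with a DLT |
|---|---|---|---|---|---|
| 0.40 | 1/2 | 1 | 57% | 77% (52%) | 77% (57%) |
| 0.40 | 1/2 | 2 | 51% | 68% | 76% (69%) |
| 0.40 | 1/2 | 3 | 46% | 58% | 72% (71%) |
| 0.40 | 1/3 | 3 | 51% | 58% | 76% (74%) |
| 0.25 | 1/2 | 3 | 14% | 24% | 36% (35%) |

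A fourth rule, waiting for 10 fully evaluable patients, leaves the base values unchanged: 62% at p = 0.40 and 22% at p = 0.25. It needs 10 + m patients enrolled.

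**What the table shows.** The rule matters most at m = 3. That is an upper case: Section 4.1 specifies marrow screening only for neuroblastoma, and with equal accrual to the two arms 3 of the first 10 would be 3/5 = 60% of the neuroblastoma patients. At m = 1 the result depends more on whether the cut-off is 0.33 or one third: dropping the patient gives 77% or 52%, on either side of the ordinary 57%. The check is also coarse with no criterion 5 patients at all. At a true rate of 40% it stays silent 1 − 0.618 = 38% of the time.

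**The case for a change.** The strongest argument for a change is that this is a protocol-level safety prompt whose denominator is undefined. In the m = 3 case the chance of firing runs from 46% to 72% by counting rule alone, and two or three sentences would settle it. The gap in the supplied text is real, and such a sentence would do no harm.

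The argument does not carry further, for three reasons.

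First, asking the sponsor to state a rule is not the same as having a better one. Counting these patients as ordinary dilutes the rate. Entering them only with a DLT selects on the outcome. Dropping them discards their non-hematologic DLTs and shrinks the denominator. Waiting for 10 fully evaluable patients delays the check. None is clearly best.

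Second, the text supports a workable reading. The check sits in the section whose variable is defined on the DDS. Criterion 5 removes hematologic events from these patients' DLT assessment. The exposure rule, the 28-day rule and the joint Sponsor and Investigator judgement in Section 10.1.3 then decide entry. That judgement leaves room for the case-by-case decision needed. The difference between Section 10.4.2 and Appendix 7 is a wording matter separate from criterion 5, and the conditional wording suits a re-run that happens only above 33%.

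Third, the absence of a rule cannot be confirmed, because RAP Module 3 was not supplied and parts of Appendix 7 are redacted.

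**Conclusion.** This is a drafting gap that the analysts and the clinical review can fill sensibly, and no change to the plan is needed. Crossing 33% leads to a model re-run. Only if the dose then fails overdose control may it be changed, and that follows review of the clinical data. In a group this small the team can see which patients came in under criterion 5 and compute the rate with and without them.

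The size rests on assumptions. At a true rate of 40%, half of DLTs hematologic and 3 of 10 patients affected, the chance of a re-run is 46%, 58% or 72% by counting rule. With 1 of 10 affected, even the direction depends on how 33% is rounded. The documents give no frequency for criterion 5 patients. The prior is redacted, so the effect on the re-run itself cannot be calculated.

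The reach is limited. Criterion 5 applies to the expansion part only, so the escalation MTD/RDE does not depend on it. SAP Section 2.5 records that the MTD/RDE was determined before enrollment was halted, Section 2.5.4 drops the planned expansion evaluation, and Section 4 confines all analyses to escalation. No reported result turns on the counting rule.
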